4. STUDY POPULATION

4.1 Population (base)

The study population consists of patients with a life-limiting illness, receiving palliative care from nursing teams that work at two large homecare organizations in Utrecht, the Netherlands. Patients of different sex and age categories will participate in this study. All patients live at home, in the region of Utrecht and suffer from a wide range of life-limiting illnesses. Family caregivers participating in this study are the primary caregiver of the patient and may live in other regions of the Netherlands than the patient, since they are not bound by the range of a homecare organization.

Nursing teams usually consist of nurse assistants (NAs), registered nurses (RNs), specialized nurses (SNs) and nurse practitioners (NPs). All types of nurses have different educational backgrounds and therefore different job descriptions and responsibilities. NAs have three years of practical educational training after receiving their diploma. RN can be educated at an intermediate or a higher level. An intermediate RN receives at least 6400 hours of practical and theoretical education and RN with a higher level of education receives at least 6720 hours of education, of which a minimum of 1535 hours of theoretical courses and 2300 hours of on-the-job instruction. Both educational programmes take 4 years to complete, however, only the higher level of nursing education results in Bachelor of Nursing degree. Additionally, both RN can specialize in a certain health field, for example to become a district nurse (DN) or oncology nurse, which are SNs. RN with a higher level of nursing education can become NPs by completing a Master's of Advanced Nursing Practice, which comprises of 2 additional years of practical and theoretical education(30,31).

4.2 Inclusion criteria

Patients are eligible if:

1. patient is 18 years or older.
2. The patient is diagnosed with a life limiting illness or frailty syndrome with a life expectancy of less than a year, estimated by the nursing team, based on the Surprise Question.
3. The patient lives at home.
4. The patient suffers from at least 1 symptom identified by means of the problem list of the Distress Thermometer.
5. The primary caregiver/informal caregiver is aged over 18 and able to speak and read Dutch.

A member of the nursing team is eligible if:

1. He/she working as a nurse assistant, registered nurse, specialized nurse, nurse practitioner or palliative care specialist consultant.
2. He/she is 18 years or older.
3. He/she works for at least 16 hours a week.

A nursing team of a participating homecare organizations is eligible if:

1. The nurses that are part of the nursing team are motivated to participate in the study.
2. The Nursing team has a total of ten or more patients under their care suffering from a life-limiting illness.

Chaplains, GPs, paramedics, social workers, and other healthcare professionals are eligible if:

1. He/she is 18 years or older.
2. He/she actively collaborates with one of the included nursing teams.

4.3 Exclusion criteria

Patients diagnosed with cognitive impairment and/or patients unable to read and speak Dutch, will be excluded from the study.

4.4 Sample size calculation

As concluded by Adams et al., there is always a certain degree of uncertainty in estimating the magnitude of the intraclass correlation coefficient (ICC) for cRCTs beforehand(32). Therefore, the following calculation aims to provide the most accurate estimate of the required sample size, in order to demonstrate an effect. Based on our experience required during KWASA, a pilot study, primary nursing teams identify on average twenty patients with a life expectancy of one year or less. Hence, we expect the inclusion of twenty patients per nursing team to be feasible during this study. To estimate the number of clusters as accurate as possible, we considered different ICCs and different effect sizes for the intervention group(I). We calculated the number of clusters necessary assuming a power of 80%, an alpha of 5%, an effect size of 30% in the control group (C) and an effect size of 40% and 60% in the intervention group. Table 1 shows an overview of the results of our calculations.

Table 1. Overview results sample size calculation with different ICC and effect size.

ICC	N patients	I	C	N clusters
0.02	20	0.4	0.3	26
0.01	20	0.4	0.3	23
0.005	20	0.4	0.3	21
0.001	20	0.4	0.3	20
0.02	20	0.6	0.3	5
0.01	20	0.6	0.3	4
0.005	20	0.6	0.3	4
0.001	20	0.6	0.3	4

* ICC = Intraclass correlation coefficient. N patients = Number of patients in the cluster.
I = Intervention group. C = Control group. N cluster = Number of clusters.

According to our calculation a total of 20 clusters in each arm is the best fit for this study, assuming an effect size of 40% and an ICC of 0.001. A higher ICC results in a limited number of extra clusters, therefore, a total of 800 patients divided into 40 clusters is in our opinion the most appropriate. All calculations have been conducted with help of a methodologist from the Julius Centre and by means of the ClusterPower package of RStudio (Vienna, Austria), version 2022.12.0+353.

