5. METHODS

5.1 Study parameters/endpoints

5.1.1. Main study parameter/endpoint

The main study parameter is “perceived symptom control of patients and family caregivers dealing with a life-limiting illness, after one month of implementing the SMEtH-intervention”. Perceived symptom control is defined as the perception of symptom control by a patient, assessed at enrolment and after one month by a one item question: “Do you feel your symptoms are under control? Yes/ No?”. The endpoint of one month has been chosen to limit the number of missing data due to death of participating patients.

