5.4. Replacement of individual subjects after withdrawal

After the withdrawal of a patient, the patient will specifically be asked if the collected data up to that point may be used for the purposes of this study. If not, data regarding this patient will be removed from the database.

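### The 80% power in section 4.4 treats every enrolled patient as a one-month answer; on Table 1's apparent method it survives only about 4% loss, and no expected loss is stated.

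*Protocol*

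**What the plan says.** Protocol section 4.4 starts from the pilot study, in which "primary nursing teams identify on average twenty patients with a life expectancy of one year or less". It goes on: "we expect the inclusion of twenty patients per nursing team to be feasible during this study". Twenty then enters Table 1 as the number of patients in the cluster. The proportions are described as "an effect size of 30% in the control group (C) and an effect size of 40% and 60% in the intervention group", with 80% power and 5% alpha. The row chosen is the one "assuming an effect size of 40% and an ICC of 0.001", which needs 20 teams per arm. Hence "a total of 800 patients divided into 40 clusters is in our opinion the most appropriate".

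Other sections foresee that some patients will give no usable one-month answer:

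- Section 5.1.1: "The endpoint of one month has been chosen to limit the number of missing data due to death of participating patients".
- Section 5.3: consent can be withdrawn at any time.
- Section 5.4, on patients who withdraw and are asked whether their data may still be used: "If not, data regarding this patient will be removed from the database".
- Section 6.1: missing data will be multiply imputed.

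Section 7.2 keeps the cohort open to new eligible patients during the study. The document supplied as the SAP is a data management plan. It ticks that a missing-data policy exists (section 2.5), but it neither describes the policy nor discusses sample size.

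**The concern.** Identified, included and analysed patients are three different counts, and section 4.4 uses one number for all of them. The power of the primary comparison depends on the last count: patients who answer the symptom-control question at one month. In a population judged to be in its last year of life, that count will be lower than the number enrolled by some amount the protocol does not estimate.

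What is at stake is the 80% figure itself. If the result is null, readers will weigh it as coming from a trial with 80% power for a 10-point difference. That weight is right only if nearly all enrolled patients answer.

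**Working it through.** **Inputs (all from section 4.4).** Proportions 0.30 and 0.40; alpha 5%, taken as two-sided because the text does not say; target power 80%; ICC 0.001; m = 20 patients per team; k = 20 teams per arm.

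**Method.** Section 4.4 names a software package but no formula, so the formula was inferred by matching Table 1.

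- Design effect: DE = 1 + (m − 1) × ICC
- Standard error: SE = √[2 p̄(1 − p̄) × DE / (k m)], with p̄ the mean of the two proportions
- Power: noncentral t with 2(k − 1) degrees of freedom and noncentrality (difference)/SE, with k rounded up

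**Reproducing Table 1.** This gives 26, 23, 21, 20 teams per arm for 40% versus 30%, and 5, 4, 4, 4 for 60% versus 30%. All eight rows match with no loss term. An unpooled variance matches seven of eight (4 instead of 5 in the row with ICC 0.02 and 60%). Normal-approximation versions do not match.

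**Power with no loss.** p̄ = 0.35, so 2 × 0.35 × 0.65 = 0.455. DE = 1 + 19 × 0.001 = 1.019. SE = √(0.455 × 1.019 / 400) = 0.0340. Noncentrality = 0.10/0.0340 = 2.94 on 38 df; critical value 2.024. Power = 81.7%.

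**Where the slack comes from.** Before rounding, the method needs about 19.2 teams per arm. Rounding up to 20 is the only source of the 1.7 points above 80%.

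**Break-even.** With k = 20 fixed, 80% power needs m = 19.14 answers per team. 19.14 × 40 ≈ 766, so about 34 of 800 patients can be lost (34/800 = 4.3%). With the unpooled variance the break-even is 18.93 per team, about 757 answers and 43 lost (5.4%).

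**Power under assumed loss.** The documents give no rate, so the rates below are assumptions. Loss is spread evenly over teams: m = 20 × (1 − loss), k = 20, ICC 0.001.

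| Loss by one month | Answers | Power, pooled | Power, unpooled |
|---|---|---|---|
| 0% | 800 | 81.7% | 82.1% |
| 3% | 776 | 80.5% | 80.9% |
| 5% | 760 | 79.7% | 80.1% |
| 10% | 720 | 77.6% | 78.0% |
| 20% | 640 | 72.8% | 73.2% |

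**Enrolment that would yield 766 answers from 40 teams.** 766/0.95 = 807; 766/0.90 = 852; 766/0.80 = 958 (rounded up).

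**The case against.** - **No loss rate is documented.** This stands, and it limits the claim. A reader might infer that any realistic loss takes the design below 80%. The documents do not support that: 3% loss still leaves 80.5%. Section 5.1.1 speaks of limiting missing data and gives no number. The surprise question fixes neither a median survival nor a hazard. Under an assumed constant hazard, a median of 12 months implies 1 − 2^(−1/12) = 5.6% deaths in the first month, and a median of 18 months implies 1 − 2^(−1/18) = 3.8%. These fall on either side of the margin.
- **The margin is not exact.** It rests on an inferred formula with equal team sizes, and it ignores the planned covariate adjustment. The unpooled version allows about one percentage point more. About 4 to 5% is as fine as the figure should be read.
- **Imputation.** Symptom control is also asked at enrolment (5.1.1) and, by section 5.2, at three and six months. For survivors who miss only the one-month form, imputation may recover part of the information. It recovers little for patients who die, and 4.4 does not offer it as a size allowance.
- **Open cohort.** Section 7.2 lets teams go on enrolling, which is an obvious way to make up losses. It is not stated as replacement of lost patients, and 800 is not defined as a count of one-month answers.
- **The shortfall may be small, and precision will be visible.** This is fair. At 5% loss the power is 0.3 points under target, and section 6.1 promises a 95% confidence interval. Section 4.4 also admits uncertainty about the ICC, but that is a separate matter from loss.

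**Conclusion.** The omission is real and modest in size. There is no arithmetical slip: 20 × 40 is 800 and Table 1 reproduces. What is missing is a stated difference between enrolled and analysed patients. As written, the 80% holds only if at least about 766 of 800 patients (about 95 to 96%) give a one-month answer. Beyond that, the cost is about 2 points below target at 10% loss and about 7 points at 20%.

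This rests on the chosen ICC of 0.001, twenty enrolled patients in every team, even loss across teams and the inferred method. The chosen ICC is the favourable case: at the other ICCs in Table 1 (0.005, 0.01, 0.02), 20 teams per arm give 78.9%, 75.5% and 69.1% before any loss. How far the trial will fall short, or whether it will, cannot be said from the documents.

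**What to change.** In section 4.4:

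1. Give two numbers: patients enrolled, and patients expected to have a one-month answer.
2. State the expected one-month loss and its source, using the pilot study if it recorded one.
3. Restate the power at the expected number analysed. For example, at an assumed 10% loss: 800 enrolled, 720 analysed, power about 78% at ICC 0.001.

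As an alternative to step 3, state that enrolment under section 7.2 continues until about 766 one-month answers are reached within the planned period.

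Restating the power needs only protocol wording and no extra patients; its price is a stated power a few points lower. The alternative keeps 80% but may need more than 800 enrolled: about 852 at 10% loss, or 852/40 = 21.3 per team, compared with the twenty that section 4.4 considers feasible.

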5. METHODS

5.1 Study parameters/endpoints

5.1.1. Main study parameter/endpoint

The main study parameter is “perceived symptom control of patients and family caregivers dealing with a life-limiting illness, after one month of implementing the SMEtH-intervention”. Perceived symptom control is defined as the perception of symptom control by a patient, assessed at enrolment and after one month by a one item question: “Do you feel your symptoms are under control? Yes/ No?”. The endpoint of one month has been chosen to limit the number of missing data due to death of participating patients.

5.1.2. Secondary study parameters/endpoints

The Quality of life of patients is assessed at enrolment, at one, three and six months by means of the EORTC QLQ C15 pal(33). This is a 15-item questionnaire developed by the European Organisation for research and treatment of cancer Quality of Life Group. The questions are answered on a scale from 1 to 4, in which the number 1 refers to “not at all”, 2 refers to “a little”, 3 refers to “quite a bit” and 4 refers to “very much”. The EORTC QLQ C15 pal is a shorted version of the original EORTC QLQ C30 pal, which is specifically developed for palliative care. To optimize the feasibility of measures, this shortened version will be used to reduce the risk of missing items and decrease the burden on participating patients.

Symptom burden of patients is assessed at enrolment, at one, three and six months by means of the Utrecht Symptom Diary Four Dimensional (USD4D), which is a patient reported outcome measure (PROM)(34). The USD4D comprises of questions regarding the physical, psychological, social, and spiritual dimension, which are rated on a scale from 0-10 (0 = symptom is absent to 10 = severity symptom is the worst imaginable).

Primary caregiver burden is defined as the perceived burden of the individual that is faced with the primary responsibility of taking care of a disabled friend or loved one. The primary caregiver burden Is assessed at enrolment, one, three and six months by means of the Self Rated Burden Scale, which is a one item numerical scale answering the question “How do I perceive the care for my loved one at the moment?”(35–38). The question is answered on a scale of 0 to 10, in which 0 refers to “not at all straining” and 1 refers to “much to straining”. In

addition, the perceived burden of informal care (Dutch: Ervaren Druk Informele Zorg (EDIZ)) will be used, assessing aspects of informal care contributing to the perceived burden(39).

The EDIZ is developed for the use in caregivers of patients suffering from dementia at home, however, this measurement instrument is widely used to assess the level of burden of caregivers of patients with a life-limiting illness. This instrument contains 9 statements to which patients must answer “no!”, “no”, “more or less”, “yes” or “yes!”.

Current symptom management practices, roles and responsibilities, collaboration, communication, and competences are assessed by means of a questionnaire for all participating nurses and GPs at enrolment and after six months.

5.1.3. Other study parameters

The following demographic characteristics will be collected of all participating parties:

- Patient demographics: age, gender, marital status, education level, employment status (retired, unemployed, employed), (past) illness, type of employment (in the past), duration of illness, treatment, phase of illness, comorbidity, performance status (KPS), time under nursing care, number of visits per day/week. These demographics will be collected by means of a questionnaire at baseline.
- Primary caregiver demographics: age, gender, education level, role, employment status assessed at enrolment. These demographics will be collected by means of a questionnaire, at baseline, three, six and twelve months after enrolment.
- Nurse demographics participating in individual assessments: age, gender, education level, employment status (fulltime/parttime), duration of current employment at enrolment. These demographics will be collected by means of a questionnaire, at baseline, six and twelve months after enrolment.
- GP demographics: age, gender, employment status (fulltime/parttime), duration of current employment at enrolment. These demographics will be collected by means of a questionnaire, at baseline.
- Nursing team demographics: education level, local collaborations with GP and paramedics, symptom management practices at enrolment. These demographics will be collected by means of a questionnaire, at baseline, six and twelve months after enrolment.

The demographics mentioned above will also be used during the process evaluation that is part of phase four of this study.

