1. INTRODUCTION AND RATIONALE

The majority of patients with a life-limiting illness experience symptoms, impairing the quality of life(1). In 2017, a total of 150.000 individuals died in the Netherlands, of whom the vast majority had cancer (41%), cardiac disease (24%) or dementia (16%)(2). The most common experienced symptoms during the last phase of life are fatigue, pain, lack of energy, weakness, lack of appetite and dyspnoea(3,4). The intensity of these symptoms increases as death approaches, in particular the last two months of life(5). To improve the quality of life of patients with a life-limiting illness and family caregivers, adequate palliative care (PC) has proven to be essential(6–8). The World Health Organisation (WHO) defines PC as *“an approach that improves the quality of life of patients (adults and children) and their families who are facing problems associated with life-threatening illness. It prevents and relieves suffering through the early identification, correct assessment and treatment of pain and other problems, whether physical, psychosocial, or spiritual”*(9). Multiple studies have shown that PC interventions are associated with a lower symptom burden, greater advance care planning, fewer hospitalizations, lower healthcare expenses, enhanced communication between healthcare professionals and patients, enhanced emotional support, higher patient satisfaction and even improved survival(6,10–14).

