5.2. Study procedures

Firstly, this study will start with the assessment of team characteristics, to develop a suited implementation strategy that fits the team and local context but does not influence the fidelity of function. Depending on the composition of the team, education levels and competences in the team, education and training content will be established by a team of coaching experts,

consisting of independent NPs and GPs with extensive experience in PC and PR. The intervention group will be educated in identifying patients with PC needs and will be taught how to apply PR in a four-day training with practical assignments. After two weeks of providing this four-day training to the nursing team, team coaches will be coached by means of a coaching on the job trajectory once a fortnight by the team of expert coaches. Team coaches that will be trained work as NP or SN within one of the organizations and are teamed up with RNs of the general nursing team. The team coaches will perform day to day coaching on the job. The implementation of the intervention will take approximately one month and will be planned in collaboration with the teams and the coaches.

Additionally, nurses who are enrolled in the study will be invited to complete questionnaires individually at enrolment and at six months about their own current symptom management practices, roles and responsibilities, collaboration, communication, and competences.

Secondly, the research team will perform an assessment of baseline measurements in participating patients and request to complete a questionnaire regarding demographic characteristics. The assessment of baseline measurements will be performed by post, mail, telephone, or teleconsulting depending on what is the most suitable and least burdensome for the patient. Subsequently, patients will complete at one-, three- and six-months a questionnaire containing questions regarding symptom control, quality of life and symptom burden. If these questionnaire reveals that a patient does not suffer from any symptoms, it will be excluded from the study. However, the excluded patients will be asked to complete the Lastmeter questionnaire to detect symptoms that may develop at a later stage, to be able to reconsider their inclusion in the study. After each questionnaire and/or assessment patients will be offered support of a NP, specialised in PC to talk about possible thoughts or concerns raised by completing the questionnaires.

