6. STATISTICAL ANALYSIS

6.1. Primary study parameter(s)

To determine the effect of the SMEtH-intervention on the perceived symptom control after 1 month of patients of each nursing team, a mixed effects logistic regression analysis will be conducted. We will control for the following baseline measurements: age, gender, primary diagnosis, and performance status. Missing data are imputed using multiple imputation (MICE package in R) or if necessary, Bayesian imputation and analysis (Joint AI package in R). The quantitative data will be presented as odds ratio and 95% confidence interval (CI) in tables and graphs for the visualization of the results. Additionally, all analyses of primary and secondary study parameters are conducted by means of the statistical program RStudio, version 2022.12.0+353. (Vienna, Austria), and are considered statistically significant if $\alpha \leq 0.05$.

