6.2. Secondary study parameter(s)

Primary caregiver burden, symptom burden and quality of life of patients will be analyzed longitudinally using joint models for longitudinal analyses per symptom. Due to the fragility of the population, censoring of data will increase over time. Therefore, we will control for death, as well as age, gender, primary diagnosis, and performance status. Additionally, subgroup analyses for gender, age and primary diagnosis will be conducted for each secondary study parameter.

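### The primary model omits phase of illness, so any arm difference in nearness to death that remains after adjustment for performance status and diagnosis would bias the odds ratio

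*Protocol*

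**What the plan says.** - **Collected.** Protocol 5.1.3 lists among the patient baseline items "duration of illness, treatment, phase of illness, comorbidity, performance status (KPS), time under nursing care". No categories or definition of phase of illness are given.
- **Primary model.** Section 6.1, a mixed-effects logistic regression: "We will control for the following baseline measurements: age, gender, primary diagnosis, and performance status". The project abstract in the data management plan (the document supplied as the SAP) names the same four covariates.
- **Secondary models.** Section 6.2, joint longitudinal models: "Therefore, we will control for death, as well as age, gender, primary diagnosis, and performance status".
- **Rationale.** Section 1: "The intensity of these symptoms increases as death approaches, in particular the last two months of life".
- **Endpoint.** Section 5.1.1: a yes/no answer on whether symptoms feel under control, "assessed at enrolment and after one month by a one item question".
- **Enrolment.** Under 5.2 teams are randomised within organisation and told the result. Under 7.2 the attending nurse and a team contact person screen patients, the nurse approaches them, and enrolment stays open during the study. Section 5.2 adds, for one arm only: "The intervention group will be educated in identifying patients with PC needs".

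**The concern.** In a trial that randomises patients, leaving out a prognostic covariate costs some precision but does not bias the comparison. Here teams are randomised, and patients are then chosen by nurses who know their team's arm. One arm has been trained to find patients with palliative needs. If that training works, it can change the point in the illness at which patients enter, and in that arm only.

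If intervention teams enrol patients further from death, symptoms may seem better controlled at one month without any effect of the method. If they enrol patients nearer to death, a real effect may be hidden. Performance status and diagnosis will absorb part of such a difference. Phase of illness could absorb more and is already on the baseline form, but it is not in the model.

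**Working it through.** **1. The plan's own figure.** Inputs from 4.4: 40% v 30%, 20 patients per team, 80% power, 5% alpha (taken as two-sided), ICC 0.001. Pooled proportion 0.35, so the variance term is 2 × 0.35 × 0.65 = 0.455. Design effect 1 + 19 × 0.001 = 1.019. A t test on 2(k − 1) degrees of freedom gives k = 19.20, rounded up to 20 per arm. The same method reproduces all eight rows of Table 1. No input depends on the covariate list, so the sample size is not in question. The design odds ratio is (0.40/0.60)/(0.30/0.70) = 1.56.

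**2. Bias with no adjustment.** The documents give no phase distribution, phase effect or imbalance, so these are assumptions: 30% late phase in the control arm, 30% yes in the control arm, no treatment effect. With a late-phase odds ratio of 0.5, solving 0.7·p0 + 0.3·p1 = 0.30 gives p0 = 0.3406 and p1 = 0.2053. With 20% late in the intervention arm, the yes rate is 0.8 × 0.3406 + 0.2 × 0.2053 = 0.3135. The odds ratio is (0.3135/0.6865)/(0.30/0.70) = 1.066. Over late-phase odds ratios from 0.67 to 0.33:

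| Arm difference | Fewer late in intervention | More late in intervention |
|---|---|---|
| 5 points | 1.019 to 1.049 | 0.981 to 0.952 |
| 10 points | 1.039 to 1.100 | 0.962 to 0.906 |
| 20 points | 1.079 to 1.206 | 0.925 to 0.816 |

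Chance alone gives the arm difference an SD of √[(2 × 0.3 × 0.7/400)(1 + 19ρ)], which is 3.3 points at ρ = 0.001 and 4.5 points at ρ = 0.05. A gap of 10 points or more would therefore point to selection.

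**3. What performance status already removes.** Take a late-phase odds ratio of 0.5 and more late-phase patients in the intervention arm. The unadjusted values are 0.94 (10 points) and 0.88 (20 points). A performance-status proxy correlated 0.4 to 0.8 with nearness to death moves them to 0.95–0.98 and 0.89–0.95.

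**4. At trial size.** Assumptions: 400 per arm, ICC about 0, 37% yes outside a late phase and 19% in it, 40% late in the control arm (0.6 × 0.37 + 0.4 × 0.19 = 0.298), performance status correlated 0.5 with phase and in the model. Simulation with 1,500 to 3,000 trials per scenario:

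| Scenario | Without phase | With phase |
|---|---|---|
| No effect, 10 points fewer late in intervention | OR 1.07, about 6–8% false positives | OR 1.00, about 5% |
| No effect, 20 points fewer | OR 1.14, 14% | OR 1.00, about 5% |
| Conditional OR 1.57, 10 points more late | power 68–69% | power 83% |
| Conditional OR 1.57, balanced | power about 82–83% | about 83–84% |

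With a correlation of 0.7 the 20-point null case still gives 1.10.

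**5. If phase is only a proxy.** Step 4 makes phase itself the cause of the outcome, so adding it must restore 1.00. Suppose instead that continuous nearness to death is the cause (log odds ratio −0.4 per SD), performance status correlates 0.5 with it, and the scale behind a two-level phase correlates 0.5 to 0.7. Shift the intervention arm 0.26 SD further from death. With 40% late in the control arm, the recorded phase gap is about 0.386 × 0.26 × (0.5 to 0.7), or 5 to 7 points. The null odds ratio is about 1.08 with performance status and 1.06–1.07 with phase added. Other choices of this kind give about 1.06–1.09 and 1.03–1.08.

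**6. If labelling differs by arm.** Keep the arms truly balanced, but record 10 (20) points too many intervention patients as late. In the step 4 model, adjusting for phase then gives 1.08 (1.15), against about 1.00 without it. In the step 5 model at correlation 0.5, 20 points of over-labelling gives about 1.04–1.05.

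**The case against.** The strongest case against has four parts.

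- **The model is not blind to nearness to death.** Performance status and diagnosis are in it, and step 3 shows that they remove part of the bias. This stands. A reader might infer that every arm difference in nearness to death passes into the odds ratio; the documents do not support that. Only the residual difference does.
- **The rationale does not mention phase of illness.** It ties symptom intensity to approaching death, while the endpoint is a yes/no perception of control. Phase is undefined, and every patient already has an expected life of under a year. This stands: phase is a plausible proxy and no more. The inference that adjusting for it would return a null result to 1.00 holds only if phase is itself the cause (step 4 against step 5).
- **Adjustment could add bias.** Section 5.2 says that local nurses who know their allocation collect data, and an undefined label may be applied differently after training. Step 6 shows that the harm could match the benefit. This stands against an undefined phase variable. It is met by one definition applied in the same way in both arms, with the unadjusted-for-phase result alongside.
- **The root problem is unblinded enrolment after allocation, and other baseline values are missing too.** Symptom control at enrolment is measured and also absent from the 6.1 list. Both are true, but neither is a reason to leave phase out.

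Extending the point to 6.2 with equal force is also not supported, because those models already control for death.

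**Conclusion.** The point holds in a limited form. Phase of illness is collected and left out of the primary model, and the enrolment procedure gives a concrete reason why the arms might differ in nearness to death. A difference remaining after performance status and diagnosis would bias the primary odds ratio.

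Its size and direction cannot be derived from the documents. On the assumptions above, and with performance status adjusted, a true null appears as about 1.03 to 1.07 in the 10-point cases (or the reciprocal direction) and up to about 1.14 at 20 points. Adding phase shrinks this, by little if phase is a weak proxy. If the arms are balanced, the gain is about 1 point of power.

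A reader might conclude that the planned analysis is biased in favour of Palliative Reasoning. Nothing in the documents shows that an imbalance will occur or which arm it would favour. No stated figure is wrong, and 20 clusters per arm is unaffected. The change is worth making because it is cheap and because adding phase after an imbalance has been seen would look data-driven.

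**What to change.** 1. In 5.1.3, state one definition of phase of illness with its categories. Have it recorded at enrolment, in the same way and by the same kind of assessor in both arms.
2. In 6.1, add phase of illness at enrolment to the covariates of the mixed logistic model and to the imputation model.
3. Report phase of illness by arm in the baseline table (6.3).
4. Prespecify the 6.1 model without phase as a sensitivity analysis, in case labelling differs by arm. If the two results diverge, say so and do not choose between them afterwards.
5. In 6.2, adding phase is optional.

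**Cost.** One or two model parameters that overlap with performance status, a short definition with instructions to assessors, and one extra model run. The item is already collected and the sample size does not change. The amendment should be dated before any outcome data are examined by group. It does not cure selection at enrolment; it only limits how much of it reaches the odds ratio.
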